In exceptional circumstances where baseline clinical data has been collected prior to the start of treatment either through clinical care or ethically approved research projects (including a cohort of subjects initially recruited to this study on the understanding that it was a non-regulated observational study) subjects already receiving ETI may be recruited to this study and undergo on-treatment visits. Any additional patient data can only be added with written informed consent from the patients/parents concerned.

P.I. [name]

All subjects must have a signed informed consent form and/or signed assent form when appropriate, as determined by the subjects age and individual site and country standards.

Male and female participants of childbearing potential must agree to adhere to contraception requirements as detailed in the local ETI SmPC and in line with the standard of care.

Exclusion criteria

Patients not willing to comply with study procedures or assessments.

Individuals on clinical trials of investigational CFTR modulators.

Clinical instability at baseline assessments. Subjects undergoing an active exacerbation and at the beginning of their treatment should be excluded from the study as this is likely to skew the data.

Any contraindication to ETI treatment as per the local approved SmPC.

Severe hepatic impairment.

Pregnant and breastfeeding women.

Inclusion and Exclusion Criteria for Extension Study

Inclusion criteria

Children and adults with CF who have completed two years participation on the parent study, and are willing to provide informed consent for continued data and bio-sample collection for a period of five years.

Exclusion criteria

Participants not willing to comply with study procedures or assessments.

Individuals on clinical trials of investigational CFTR modulators.

Drug Interruption or Discontinuation of ETI

If a patient experiences a drug interruption, discontinues ETI and/or is prescribed TEZ/IVA, LUM/IVA or IVA, they can continue trial participation.

Advanced Testing v Standard Testing for the Parent Study

As outlined in Table 5, we will have a standard and advanced testing group for the parent study. In addition to all elements of the standard testing group, the advanced testing group will undergo:

- Ultra-low dose spirometry-controlled CT scanning
- Sputum collection
- Nasal lavage collection

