Nasal lavage will be collected as previously described(21) at baseline, 6 months and one year. Briefly, 10ml of sterile isotonic saline will be slowly injected into each nostril sequentially using a 10ml syringe while the subject occludes their soft palate and reclines their head. The saline is allowed to remain in the nasal airways for 10 seconds before being drained into a sterile collection container by the subject leaning forward. If a clinical specimen is required, 5ml of fluid will be sent separately to the local microbiology lab for routine processing. Lavage fluid will be put on ice and transferred to the laboratory for aliquoting and immediate freezing at -80°C. An aliquot of the nasal lavage fluid will be mixed with an RNA preservative (RNAlater) and frozen at -80°C for later 16s shotgun sequencing. Nasal lavage will be performed in individuals 12 years and older.

Airway Infection

Microbiological processing of samples will be completed as per usual clinical practice at clinical microbiology labs at each clinical site. As part of the study, consent will be sought from parents to access historic and current clinical microbiology sample results uploaded to CFRI and the UK CF Registry. Using a similar approach to national registries we will track the percentage of individuals culturing positive for particular organisms prior to and over the course of the study period. In addition, we will analyse trends at an individual level prior to and during treatment with ETI. We will be able to compare pulmonary function and imaging findings collected via RECOVER to clinically collected airway infection data.

Microbiome Analysis

DNA extraction and processing will be performed by our collaborators at the APC Microbiome Ireland in Cork, Ireland who have extensive experience with gut and lung microbiome projects in CF(139-141). Samples will undergo deep shotgun sequencing using the Illumina NextSeq platform. Detailed descriptions of microbial community composition and metabolic profile will be obtained.

Breath Sample Collection

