The main foreseeable risk factor in this part of the study is the inability to collect a sputum specimen. Many patients, especially younger or healthier ones may not routinely produce sputum on a regular basis. We further suspect that, in light of the significant improvements in clinical outcomes demonstrated already for Kaftrio, that many individuals will go from being sputum producers to non-producers on treatment. We will work closely with the clinical teams to ensure that sputum specimens are optimized in terms of the split between laboratory and research processing. Each clinic has their own mechanism for trying to facilitate sputum production either at clinics or annual assessment – we will work with teams to ensure that saline induction, where used, can be facilitated by the research team to try to ensure a suitable sample sputum volume can be collected for all uses. We are aiming to collect 4 sputum samples over 2 years for RECOVER, with the baseline and year one samples prioritized. Where possible the research team will work with the subjects and clinical teams to ensure that all efforts are made to obtain a sufficient sample volume at these timepoints in particular, including sputum induction. The use of the TETRIS sputum processing protocol will mean that it is acceptable to use

P.I. [name] spontaneously produced and induced sputum interchangeably when obtaining samples. This will greatly facilitate optimal sampling.

We expect that an incomplete set of samples will be collected and have factored this into our study calculations in terms of numbers and budget. With a recruitment of 150 individuals to the advanced group we would ideally expect 600 sputum samples and 414 nasal lavage samples to process (1014 total). In reality we estimate that it is likely that we will have 90% of individuals produce one sputum sample, 80% to produce 2 samples, and 70% to produce 3 samples and 60% to produce 4 samples. We estimate that 80% of eligible individuals will produce one nasal lavage sample, 70% two samples and 60% three samples. The main foreseeable risk factor with nasal lavage is aspiration of isotonic saline. In practice this is a very similar procedure to sinus rinse which is commonly performed by many people with CF on a daily basis where we see almost no adverse effects in those who learn how to do the procedure. It is likely that some people may find this an uncomfortable or awkward procedure and elect not to do it.

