In this multi-centre longitudinal study of subjects starting on ETI we will be examining many different outcomes, and so sample size requirements are different for different aspects. Patients will be recruited to the study up to a cap of 254 participants. On the basis of the phase two trials of ETI(57), we are expecting a significant treatment effect in line with what was previously seen with Ivacaftor treatment in individuals with a gating mutation, and in excess of what was seen with Lumacaftor/Ivacaftor in individuals homozygous for F508del. Our sample size is higher than we expect to be required for most outcomes where data exists (see tables 11, 12, 13 below). We have aimed high deliberately for a number of reasons. Firstly, clinical research naturally carries risks in terms of adequacy of data collection. Secondly, we are keen to ensure that outcome measures can be cross referenced between each other and with previously collected, yet to be collected and data and samples. This will require excess power. With missing or incomplete samples across different outcome measures, complete datasets on a core number of individuals will necessitate collection in a larger cohort. Thirdly, this study represents a unique opportunity, which may not be replicated, to collect this data, and promises very significant insights into CF disease pathogenesis and response to therapies. In light of this, a large sample size with adequate sample collection we feel is important. Where data is available, we have performed sample size calculations (table 10). Where data is not available, we present a summary of key studies and evidence in the area.

Power and sample size calculations were produced for LCI as a main primary endpoint, using the GLMPOWER procedure in SAS 9.3 (Table11, Figure 5). A range of scenarios were considered for standard deviation from 2 (expected) to 3 (conservative) and power was computed for F/F participants only and for F/F and F/M participants combined. We estimated a conservative treatment effect at 1 unit of improvement in LCI (as seen with lumacaftor/ivacaftor), and an expected treatment effect at 2 unit of improvement in LCI (as seen with lvacaftor in gating mutations).

Group	Sample Size	Std Dev	Power (1 unit)	Power (2 unit)
F/F only	166	2	91.9%	99.4%
F/F & F/M	201	2	96.4%	99.9%
F/F only	166	2.5	76.6%	94.8%
F/F & F/M	201	2.5	85.3%	98.0%
F/F only	166	3	61.0%	84.7%
F/F & F/M	201	3	70.8%	91.7%

[figure not shown]

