Figure 5 Sample size versus power for LCI. Power calculations are for an absolute difference of A) 2 LCI unit and B) 1 LCI unit between baseline and 1 year, assuming a conservative estimate for standard deviation of 3.

Endpoint	Reference Study	Comments
LCI	[name] et al(76), [name] et al(56)	Significant improvement in LCI was seen with Ivacaftor with 20 subjects and Orkambi with 206 participants
PRAGMA CT score	Rosenow et al(130)	Sample size estimates in this paper suggested 100 children required to see a 50% reduction in %disease over 3 years and 76 for an approximate halving of bronchiectasis progression over 3 years. This is in very young children with mild disease.
FeNO	[name] et al(89)	A significant increase in FeNO was seen with 15 subjects on Ivacaftor
Liver disease parameters	Rowland et al.(40)	Limited relevant data available. 10 year follow up in 84 individuals revealed significant differences in mortality. Unpublished data on 522 individuals, some of whom will be part of RECOVER has again shown significant changes in status over time and mortality.
GI inflammation	Ooi et al (32)	Significant reductions in calprotectin and M2PK seen in 16 individuals on Ivacaftor
Abdominal symptoms	Tabori et al (29)	114 subjects were studied. Significant differences in abdominal symptom scores were seen between individuals with PS and class 4 or 5 CFTR mutations and those with class 2 and PI suggesting that reported symptoms may be relatable to CFTR function in a cohort of this size

P.I. [name]

050 D		
CFQ-R	Keating et al (59)	Total recruitment was 123 participants (F508del homozygotes
		and heterozygotes with differing dose levels. Between group
		comparisons using 7-21 subjects per group showed
		significant improvements in CFQ-R compared to controls
Airway	Hisert et al (12)	Significant and sustained reductions in sputum inflammatory
Inflammation		markers were seen in 12 subjects after the initiation of
		Ivacaftor
Nasal	Muller et al(23),	Nasal inflammation in 19 individuals after IV antibiotic therapy
inflammation	McCormick et	showed a trend to improvement. Ivacaftor treatment in 153
	al(24)	individuals was associated with significant improvements in
		nasal symptom score. Data for nasal inflammation and CFTR
		modulator use is not available.
Sweat Chloride	Keating et al (59)	Total recruitment was 123 participants (F508del homozygotes
onout onionao	roading of al (00)	and heterozygotes with differing dose levels. Between group

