		comparisons using 7-21 subjects per group showed
		significant improvements in sweat chloride compared to
		controls

Table 12 Sample size examples in CF literature pertaining to RECOVER endpoints

Variable	Expected effect size	Mean	SD	Power (n=166)	Power (n=201)	Sample size for 90% power
CT scores	50% relative reduction in %disease at 2 years	2.62	2.59	62.0%	71.8%	325*
FeNO	100% increase in FeNO	8.5	5	>99%	>99%	39
GI inflammation	Reduction in stool Calprotectin by 50% (median [IQR]: 154.4 [102.1–284.2])	NA	NA	>99%	>99%	39
Abdominal scores	Reduction in CF Abd score by 5 points	19.9	5.6	89.2%	94.7%	169
CT scores	reduction by 20 points	71.2	17.3	>99%	>99%	65
Sweat chloride	reduction by 40 mmol/L	99.5	9	>99%	>99%	13
Nasal inflammation	Reduction of IL-8 by one third	1145	656	85%	92%	195

*See detailed discussion of this in Rosenow et al(105) who suggest a sample size requirement of 100 individuals to detect a 50% relative reduction in %disease at 2 years.

Table 13 Sample size calculations for RECOVER parent study where data is available

Treatment of Missing Data

To prevent loss of information and introducing potential selection biases, missing values may be imputed. Where patterns of missingness are not correlated with outcome variables, multiple imputation will be used under the missing at random assumption. Multiple imputation accounts for uncertainty in the standard errors, confidence intervals and p-values. Complete-case analyses will also be performed, and the results compared to the imputation results as a sensitivity analysis.

Descriptive Statistics

Descriptive statistics will be performed on all measured outcome variables and derived variables. A baseline table will present the demographic and clinical characteristics by treatment group and overall. Continuous variables will be summarized using means and standard deviations. Medians with interquartile ranges will be presented where appropriate. The distributions of continuous variables will be assessed to determine whether variable transformation may be required. Categorical variables will be summarised using counts and percentages.

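### Table 13 states power for CT %disease and nasal IL-8 at more participants than can be measured, and on a calculation that does not match the planned within-person change

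*Protocol*

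**What the plan says.** All figures are from the protocol.

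- **Table 13** gives each power at n=166 and n=201. Table 11 labels these as F/F only and F/F with F/M. For "50% relative reduction in %disease at 2 years" the row reads "2.62 2.59 62.0% 71.8% 325" (mean, SD, the two powers, n for 90% power). The nasal row reads "Reduction of IL-8 by one third 1145 656 85% 92% 195".
- **Advanced Testing v Standard Testing** places spirometry-controlled CT and nasal lavage in the advanced group: "In addition to all elements of the standard testing group, the advanced testing group will undergo" these procedures. The text before Table 6 offers advanced testing up to the cap in that table.
- **Table 6**, advanced row: F/F 47 (aged 6-11) and 60 (12+); F/M 17 and 26; total 150, of whom 86 are aged 12+.
- **Nasal Lavage**: "Nasal lavage will be performed in individuals 12 years and older". It is collected at baseline, 6 months and one year.
- **Risks in Airway Inflammation data collection**: "With a recruitment of 150 individuals to the advanced group we would ideally expect 600 sputum samples and 414 nasal lavage samples". It then expects 80%, 70% and 60% of eligible people to give one, two and three lavage samples.
- **Sample Size and Power**: "Our sample size is higher than we expect to be required for most outcomes where data exists", with a pointer to Tables 11 to 13.
- **Primary and Secondary Outcomes** names CT scores in a primary outcome defined as change from baseline. The data analysis text calls for methods that handle within-subject correlation.

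**The concern.** A power figure has to refer to the people on whom the outcome is measured. Tables 11 to 13 and their text make no adjustment for the advanced-group cap or for the age limit on lavage, so the CT %disease and nasal IL-8 rows are stated at numbers that the protocol's own design excludes. The sizes listed for 90% power (325 for CT, 195 for nasal) also exceed the 150 and 86 who can be measured.

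CT scores are part of the primary outcome, so a reader will use this row to judge whether the imaging aim is adequately sized. As printed, it shows neither the power of the calculation at the right n nor the power of the analysis that is planned.

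**Working it through.** **1. Attainable numbers (Table 6, advanced row)**

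- CT: F/F 47 + 60 = 107; F/F plus F/M 107 + 17 + 26 = 150.
- Nasal lavage (12+): F/F 60; F/F plus F/M 60 + 26 = 86.
- Counting the 17 F/G listed in that row but left out of its total gives 167 for CT, still below 201.
- 414 nasal samples over three visits imply 414/3 = 138 people. That conflicts with 86 (86 × 3 = 258) and is still below 166.

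**2. Standardised effects**

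- CT: 0.5 × 2.62 = 1.31; d = 1.31/2.59 = 0.506.
- Nasal: 1145/3 = 381.7; d = 381.7/656 = 0.582.

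**3. Reproducing the CT row**

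Two-sided 0.05 is assumed; the protocol does not state it. At n=166 and 201:

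- paired, SD taken as the SD of change: above 99.9% at both;
- paired, zero correlation: 99.6% and 99.9%;
- two equal groups, n as the total: 90.3% and 94.8%.

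None matches. A two-group t-test with an 11:2 split does, with the total N rounded down to a multiple of 13 (166 to 156, 201 to 195). Its noncentrality is d × √(N × 22/169):

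- N=156: 0.506 × √20.31 = 2.28, power 62.0%;
- N=195: 0.506 × √25.38 = 2.55, power 71.8%;
- N=325: 90.7%, the first multiple of 13 to reach 90%.

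The 11:2 split is inferred from this match. The protocol does not state it. It also returns the n for 90% power in the FeNO (39), 20-point (65) and sweat chloride (13) rows.

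**4. The nasal row under the same calculation**

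With d = 0.582 it gives 74.1% and 83.1%, and n=247 for 90% power, against the stated 85%, 92% and 195. The stated figures need d of about 0.667 (84.7%, 91.7%, 195), which is not 381.7/656. The row is therefore inconsistent with its own inputs if it was computed like the CT row.

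**5. Same calculation at the attainable n**

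| Row | Stated (166 / 201) | Attainable n | 11:2 calculation | Stated powers scaled by √n |
|---|---|---|---|---|
| CT %disease | 62.0% / 71.8% | 107 / 150 | 45.4% / 58.2% | 44.4% / 59.2% |
| Nasal IL-8, row inputs | 85% / 92% | 60 / 86 | 31.8% / 44.9% | n/a |
| Nasal IL-8, effect implied by stated powers | 85% / 92% | 60 / 86 | 39.8% / 55.5% | 43.7% / 59.5% |

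The last column does not use the 11:2 inference. Example for CT: 1.96 + 0.305 = 2.265; 2.265 × √(107/166) = 1.819; Φ(1.819 − 1.96) = 44.4%.

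**6. A within-person calculation at the attainable n**

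The stated SD is treated as the SD at one visit, with correlation 0, so the SD of change is √2 × SD and the noncentrality is d × √(n/2) (paired t-test):

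- CT: 95.6% at 107; 99.2% at 150.
- Nasal: 88.0% at 60; 96.5% at 86.
- Nasal at 60% yield (36 and 52 people): about 67% and 83%.

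A positive correlation between visits would raise these figures. The documents give no correlation or SD of change.

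**The case against.** **That the powers are not really at risk.** The outcome is a change from baseline, and step 6 shows a within-person test at the attainable n exceeding the stated CT powers. For nasal IL-8 it exceeds the stated figures at full yield, though not at 60% yield. Table 4 adds that %disease fell from 7.34 to 3.98 (p=0.0001) with 85 baseline and 64 twelve-month scans, although that is one year and the 12+ cohort. This stands. A reader might infer from step 5 that the study cannot deliver adequate power for CT or nasal IL-8; the documents do not support that. The low figures belong to the table's calculation, not to the planned analysis.

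**That 166 and 201 might include controls.** The CT analysis plan does mention historic controls. If they are added to 107 and 150 at the inferred split, CT power is about 50% and 65%. The gap narrows but remains, and Table 11 labels 166 and 201 by participant genotype with no mention of controls.

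**That the protocol already discloses the CT shortfall.** Table 13 prints 62-72% with 325 needed and footnotes it. That is open about power but does not correct n. The footnote gives 100 individuals at 2 years, whereas Table 12 reports the same paper as "100 children required to see a 50% reduction in %disease over 3 years".

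**That the sample-size claim survives.** A reader might take these two rows to refute the statement that the sample exceeds what most outcomes need. They do not: the other five of the seven rows list 39, 39, 169, 65 and 13 for 90% power, and the wording is limited to most outcomes.

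**Conclusion.** The point holds as an error in the table. The CT %disease and nasal IL-8 rows use 166 and 201 where the protocol allows 107 and 150 for CT, and 60 and 86 for lavage. On the calculation that reproduces the CT row, power at the attainable n is about 45% and 58%. For nasal IL-8 it is about 32% and 45% on the row's inputs, or about 40-44% and 55-60% on the effect that its stated powers imply.

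The exact values rest on two-sided 0.05 and the inferred 11:2 split. The direction does not, because power falls with n when the other inputs are unchanged. The counts rest on Table 6 and the age limit; the 414 expected samples conflict with them.

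No real power shortfall is shown. A paired analysis at zero correlation is comfortable for CT and reasonable for nasal IL-8 unless sample yield is low. The 20-point row that is also labelled as CT scores is hardly affected: 98.8% at 107 and 99.9% at 150.

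**What to change.** - Restate the CT %disease row at 107 and 150, and the nasal IL-8 row at 60 and 86, less expected missing data (for lavage, the yields given under Risks in Airway Inflammation data collection). Use the planned within-person analysis, and state alpha, the SD of change and the correlation, with a range where these are assumed.
- Correct the nasal row so that its powers and its n for 90% follow from its mean, SD and effect.
- Reconcile the 414 expected nasal samples with the 86 eligible people.
- As editorial items in the same amendment, reconcile the 2-year footnote with the 3-year entry in Table 12, and its reference number (105 is a mental health consensus statement; the PRAGMA-CF paper is 130). Relabel or explain the second CT scores row, whose mean of 71.2 cannot be on the scale of 2.62.
- The sentence on most outcomes can stay, but it should not rest on these two rows until they are recalculated.

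The cost is a recalculation and a table amendment. No procedure or recruitment target changes.

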A breath sample will be collected from a cohort of 60 subjects in the 6-11 cohort at CHI at Crumlin, CHI at Temple Street, CHI at Tallaght and Guy's and St. Thomas' NHS Foundation Trust and sent to collaborators in Amsterdam University Medical Centre (AUMC) to evaluate the changes in the composition and the function of the respiratory microbiome after the initiation of Kaftrio. AUMC have developed a novel method to standardize the procedure of trapping volatile organic compounds (VOCs) in exhaled breath onto sorbent tubes. Kaftrio is shown to have a major effect on pulmonary function, mucociliary clearance and reduction in sweat chloride test. VOCs can give insight into both the metabolic pathways and inflammation caused by microorganisms in the lungs that are commonly associated with CF.

Airway Inflammation

Aliquots of sputum supernatant ± protease inhibitors from each individual and time point will be sent to the laboratory of [name] and [name], at Queens University Belfast for analysis of inflammatory markers. Although inflammation is a major feature of CF there is no universally accepted way to measure it in subjects. On the basis of our experience and data to date, we have compiled a compendium of airway inflammation biomarkers of particular relevance to the CF lung (Table 7). The sample collection and storage plan for RECOVER will allow further expansion of this panel based on initial findings or future work.

Host defence family	Members	Method of analysis
Proteases and neutrophil products	Serine (neutrophil elastase, proteinase 3), cysteine (cathepsin S, B, L), matrix metalloproteases (MMP-8, -9, -12), myeloperoxidase (MPO)	Fluorogenic activity assays, ELISA
Antiprotease	SLPI, cleaved-SLPI, tissue inhibitor of metalloproteases (TIMP-1, -2), cystatin SN and C	ELISA, Western blotting

P.I. [name]

		, ,
Cytokines/chemokines	Interleukins -1β, -6, -8	Luminex MILLIPLEX
		multianalyte panel assays

Table 7. Host factors to be analyzed in CF sputum supernatant and nasal lavage

All data will be compiled on an on-going basis over the course of the task and inputted into the study database as samples are analyzed. We would hope, that through this comprehensive approach, and analysis of the data comparing individuals before and after treatment that we will gain important insights that could be of benefit in terms of monitoring of disease activity and burden in individuals with CF.

Fraction of Exhaled Nitric Oxide (FeNO)

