One of the reasons we selected FeNO as an outcome measure in this study was that we felt we might have individuals struggle to produce sputum samples. We will likely have less in the way of available sputum samples to use for testing NO metabolites than expected, however we do not foresee any particular issues with FeNO measurement as the technique and equipment is straightforward and the test is quick to perform.

Specific Aim 4 for Parent Study and Extension Study – Gastrointestinal Manifestations

The aim of the GI arm of this study is to gain a greater understanding of the changes in abdominal manifestations of CF on modulator therapy and the relationships between these changes and other important treatment outcomes such as sweat chloride response, nutritional outcomes and pulmonary outcomes.

Abdominal Symptom Scores

Our collaborator [name] and his team at Medizinische Hochschule Brandenburg (MHB, formerly based in Jena, Germany) have developed a specific abdominal symptom questionnaire for individuals with CF. The CFAbd score is validated in children and adults with CF and scores correlate well with ultrasound findings (28-30) and gut inflammation (unpublished). The CFAbd score has been used in investigator led studies in leading international centres and translated into 9 languages. The score can be delivered by a trained researcher for the first time in 5-8 minutes, and on subsequent occasions in 3-5 minutes. Questionnaires will be delivered at centres by the local research coordinator. Questionnaire results will be collated and centrally analyzed by post-doctoral researchers at [name]. Abdominal symptom scores will be collected in tandem with stool samples as below in table 8 for the parent and extension study. Score results will be compared between baseline and follow up visits and compared to markers of gastrointestinal inflammation, pancreatic sufficiency and microbiome community structure.

	Parent Study							Exte	ension S	tudy		
	-3/12	0	1/12	2/12	6/12	1yr	2yr	Зyr	4yr	5yr	6yr	7yr
Survey	Х	Х	Х	Х	Х	Х	Х	Х	Х	Х	Х	Х
Stool sample		Х	Х		Х		Х	Х	Х	Х	Х	Х

Table 8. Sampling schedule for CFAbd scores and stool samples.

Stool Sample Collection

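### Table 13: the power and sample-size figures for the abdominal score and nasal IL-8 do not follow from their printed effects and SDs, agree with the other testable rows, or describe the planned before/after comparison

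*Protocol*

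**What the plan says.** Under Sample Size and Power for the Parent Study, Table 13 gives for each endpoint an expected effect, a mean, an SD, the power at n=166 and n=201, and the sample size for 90% power. The expected abdominal effect is "Reduction in CF Abd score by 5 points". The two rows in question read in full "Reduction in CF Abd score by 5 points 19.9 5.6 89.2% 94.7% 169" and "Reduction of IL-8 by one third 1145 656 85% 92% 195". The row used here to calibrate the method reads "50% relative reduction in %disease at 2 years 2.62 2.59 62.0% 71.8% 325".

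The table states no test, alpha, allocation ratio or control number. In Table 11, 166 and 201 are the sizes of the F/F group and the F/F plus F/M group.

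The planned comparisons are with each person's own baseline. For the abdominal score (Specific Aim 4, Abdominal Symptom Scores), "Score results will be compared between baseline and follow up visits". For the inflammatory panel, which includes IL-8 in nasal lavage (Specific Aim 3, Airway Inflammation and Table 7), the protocol relies on "analysis of the data comparing individuals before and after treatment". Nasal lavage belongs to the advanced testing group only (Advanced Testing v Standard Testing) and to people aged 12 and over (Specific Aim 3, Nasal Lavage). Table 6 projects 86 such people.

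**The concern.** Effect, SD, n and power are tied together once a test is chosen, so rows of one table should agree with each other. Here a row with a much larger standardised effect (abdominal, 0.89 SD) carries almost the same required size as a row with a much smaller one (IL-8, 0.58 SD). The ratios that reproduce the other rows also point to two independent groups, which is not how these two endpoints will be analysed.

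At stake is whether these figures can serve as the protocol's sample-size support. The text cites Tables 11 to 13 when it says the sample exceeds what most outcomes need. A reader cannot tell which effect the abdominal row is powered for, and the IL-8 row uses sample sizes that the nasal-lavage group cannot reach.

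**Working it through.** **1. A check that assumes no particular design.** Let d = effect / SD. For any one test and allocation, the size for 90% power is close to proportional to 1/d² when N is large, so N × d² should be nearly constant.

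- CT %disease: effect 0.5 × 2.62 = 1.31; d = 1.31/2.59 = 0.506; 325 × 0.506² ≈ 83
- IL-8: effect 1145/3 = 381.7; d = 381.7/656 = 0.582; 195 × 0.582² ≈ 66
- Abdominal: d = 5/5.6 = 0.893; 169 × 0.893² ≈ 135

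Scaled from the CT row, IL-8 should need about 325 × (0.506/0.582)² ≈ 246 (printed 195), and the abdominal score about 325 × (0.506/0.893)² ≈ 104 (printed 169). The three rows cannot come from one method and their printed inputs.

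**2. Reproducing the plan's figures.** Every printed 90% size (325, 39, 39, 169, 65, 13, 195) is a multiple of 13. The method that fits, inferred and not stated, is a two-sample t-test with 11:2 allocation, two-sided 0.05, and n rounded down to a multiple of 13: 166 becomes 156 (132 + 24) and 201 becomes 195 (165 + 30). The noncentrality is d × √(n₁n₂/(n₁+n₂)), where the root is 4.506 at 156 and 5.038 at 195.

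| Row | d | Noncentrality | Computed: power / power / N | Printed |
|---|---|---|---|---|
| CT %disease | 0.506 | 2.28, 2.55 | 62.0% / 71.8% / 325 | 62.0% / 71.8% / 325 |
| FeNO | 1.70 | 7.66, 8.57 | >99% / >99% / 39 | >99% / >99% / 39 |
| 20-point row | 1.156 | 5.21, 5.82 | >99% / >99% / 65 | >99% / >99% / 65 |
| Sweat chloride | 4.44 | 20.0, 22.4 | >99% / >99% / 13 | >99% / >99% / 13 |
| Abdominal | 0.893 | 4.02, 4.50 | **97.9% / 99.4% / 104** | 89.2% / 94.7% / 169 |
| Nasal IL-8 | 0.582 | 2.62, 2.93 | **74.1% / 83.1% / 247** | 85% / 92% / 195 |

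The same method returns all six entries in Table 11's 2-unit column (99.4, 99.9, 94.8, 98.0, 84.7, 91.7). It does not return the 1-unit column: at SD 2 and n=166 it gives 61.0% against the printed 91.9%. The calprotectin row has no mean or SD and cannot be tested. Other designs miss the CT size of 325: paired 44 (2.59 taken as the SD of the difference), 1:1 168, 12:1 585, 10:3 234.

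**3. What the two printed rows would match.** The abdominal figures come back exactly with 4 points and SD 5.6, or with 5 points and SD 7.0, since both give d = 0.714. The IL-8 figures match d = 0.667 (84.8% / 91.7% / 195).

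**4. The comparison the plan describes.** For a pre/post difference, SD_diff = SD × √(2(1−ρ)) and the noncentrality is √n × effect / SD_diff. The correlation ρ is not in the protocol; 0 to 0.7 is assumed, and the printed SD is taken as cross-sectional. Size for 90% power, two-sided 0.05:

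| Endpoint | ρ = 0 | ρ = 0.7 | Printed |
|---|---|---|---|
| Abdominal, 5 points | 29 | 11 | 169 |
| Nasal IL-8, one third | 65 | 21 | 195 |
| CT %disease, 50% | 85 | 27 | 325 |

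**5. The n that applies to nasal IL-8.** Table 6, advanced group aged 12+: 60 + 26 + 0 = 86. At n = 86 and ρ = 0, SD_diff = 656 × √2 = 927.7, noncentrality = √86 × 381.7/927.7 = 3.82, and power is about 96%. The protocol expects 60% of eligible people to give three lavage samples: 0.6 × 86 ≈ 52. At 52 the noncentrality is 2.97 and power about 83% at ρ = 0; at ρ = 0.3 (SD_diff 776.2) they are 3.55 and about 94%.

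**The case against.** The strongest objection is that the 11:2 method is a reconstruction. The protocol names GLMPOWER only for LCI and gives no alpha or allocation. Within Table 13 only the CT row tests the power columns, the method misses Table 11's 1-unit column, and one row is untestable. All of that stands, so the 11:2 result should be read as the best-fitting explanation of four rows. The inconsistency itself does not depend on it: step 1 uses only the printed inputs and sizes. A one-sided normal approximation at 11:2 with unrounded n comes near the IL-8 row (85.5% / 90.8% / about 194), but one-sided versions give 73% to 76% for the CT row instead of 62.0%. No variant tried reproduces the abdominal row.

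It is also fair to say that a two-group calculation is not foreign to the whole study. The Specific Aim 2 Analysis Plan also compares CT scores with historic controls, though without a number or ratio. The design criticism therefore applies to the abdominal score and nasal IL-8, not to every row.

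A reader might infer that IL-8 power is overstated by about 10 points and the study is underpowered. The documents do not support that. The shortfall exists only against a control group that the protocol does not name for this endpoint; on a before/after basis the printed sizes are too large. The protocol also says that its sample was deliberately set high.

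Finally, the risks section for Specific Aim 3 expects 414 nasal lavage samples, which at three per person is 138 people, not 86. That needs reconciling with Table 6, but 138 is still below both 166 and 201.

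**Conclusion.** The point holds as an error in the table. The abdominal and nasal IL-8 rows do not follow from their printed effects and SDs by any single method that fits the other testable rows. Under the inferred method the abdominal row is about 9 and 5 points below what its inputs give, with 65 too many people for 90% power (169 against 104); the IL-8 row is about 11 and 9 points above, with 52 too few (195 against 247). Neither row describes the within-person comparison planned for its endpoint, and n=166 and n=201 do not apply to nasal lavage.

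Two further inferences are not supported. It is tempting to conclude that the abdominal effect is a slip for 4 points, but SD 7.0 in place of 5.6 fits equally well. And the study is not shown to be underpowered for these endpoints.

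The conclusion rests on two-sided alpha 0.05 and 11:2 allocation, both inferred from fit, and, for the pre/post sizes, on assumed correlations of 0 to 0.7.

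**What to change.** - Check the abdominal effect and SD against their source and correct whichever is wrong.
- Recompute Table 13 as a within-person pre/post calculation at the printed effects and SDs. State alpha, whether the SD is cross-sectional or of the difference, and the assumed correlation with a range. Replace the power and sample-size columns.
- Give the evaluable n for each endpoint: at most 86 for nasal IL-8 on Table 6, less expected sample loss.
- If a two-group calculation is kept for CT scores against historic controls, state the control number.
- Do not print 74.1% / 83.1% / 247 for IL-8. Those figures would be power against a control group that does not exist, at sample sizes that do not apply.

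The cost is a re-run power table and a short note on its assumptions. Recruitment, endpoints and analyses are unchanged.
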